Section of Geriatrics and Gerontology

Department of Medicine and Neurology

Emory University

[contact]

[name] MPH (Co-Investigator, Postdoc Fellow)

Department of Neurology

Emory University

[contact]

[name] (Co-investigator, Neuropsychologist)

Department of Neurology

Emory University

[contact]

[name] (Statistician)

Department of Neurology

Emory University

[contact]

PARTICIPATING STUDY SITES

Wesley Woods Health Center

Emory University Hospital Clinical Research Network

Executive Park Medical Campus

PRÉCIS

Study Title

Effects of Montelukast Therapy on Alzheimer's Disease

Acronym

EMERALD

Objectives

Our *primary objective* is to determine the safety, dose-response and target engagement of the treatment with escalating doses of Montelukast in those with mild cognitive impairment (MCI) or early Alzheimer's disease (AD) dementia.

Our *secondary objectives* are to assess the efficacy and estimate the effect size of up to 1-year treatment of Montelukast on biomarkers of neurodegeneration and cognition in MCI/early AD dementia.

Design and Outcomes

This is a double-blind placebo-controlled randomized clinical trial that compares Montelukast to placebo in individuals with MCI and early AD dementia. Our measures include cognitive function, CSF biomarkers and neuroimaging (cerebral perfusion and markers of vascular brain damage).

Interventions and Duration

The intervention includes Montelukast (10, 20, or 40 mg) or placebo. The duration of the study is 1 year.

Sample Size and Population

Our target population includes subjects who are 50 years or older with MCI and early AD dementia. Our sample size is 30 for this trial.

TABLE 1. SCHEDULE OF PROCEDURES FOR THE DURATION OF THE STUDY

Phase:	SCREEN	BASELINE	FOLLOW-UP			
Number of visits	1-2 [@]	1-2				
Months	-1	0	1.5	3	6	12
Informed Consent	X					
Cognitive screening	X					
Screening labs	X*					
CSF for biomarker and molecular analysis		X**				X [^]
Weight/Height	X	X	X	X	X	X
Blood Pressure	X	X	X	X	X	X
Safety labs			X [#]	X [#]	X [#]	X [#]
Brain MRI		X				X
Vascular function measures (PWV/PWA)		X				X
Cognitive Battery		X			X	X
Functional battery (FAQ, IADL, SPPB)		X***				X
LTE₄ testing		X			X	X
Blood for biospecimen banking		X			X	X
Time (in minutes)	60-120	150-210	30	30	120-150	120-150

^{*}: Screening labs include: CBC, CMP (BUN, Cr, electrolytes, liver function test (LFT)), B12, TSH and PT/INR.

^{**}: If subject has had a lumbar puncture (LP) within the 6 months prior to their screening/baseline visit and samples are available for measuring CSF outcomes, then no LP will be done at baseline. Otherwise, LP will be done at baseline to obtain CSF for outcome measures.

^{***}: FAQ will be skipped at baseline if already done at screening visit.

[#]: Safety labs at 6 weeks, 3, 6 and 12 months include CBC, CMP (BUN, CR, electrolytes, liver function test).

[^]: If subject did not have PT/INR done at baseline or started taking any blood thinners during the study, PT/INR will be done before LP at 12 months.

[@]: for subjects who are consented electronically and complete a portion of the screen visit virtually, a 2nd in-person visit will be conducted for parts of the screen visits that cannot be done remotely.

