4.2. EXCLUSION CRITERIA

- (1) Intolerance to Montelukast;
- (2) Current diagnosis of bronchial asthma or exercise-induced bronchospasm **and** currently on Montelukast or other leukotriene receptor antagonists (Zafirlukast, Pranlukast);
- (3) Liver disease (elevated liver enzymes ($>2x$ normal): ALT, AST, alkaline phosphatase, total bilirubin);
- (4) Renal disease (Creatinine >2.0 mg/dl), platelets<50,000/ μ l, or INR>1.9;
- (5) Diagnosis of any neurological or psychiatric disorders that affects cognition such as uncontrolled depression, schizophrenia, Parkinson's disease or use of anti-Parkinsonian therapies (unless used for essential tremor), multiple sclerosis, or other active medical condition that in the judgment of the study physicians would affect the safety of the subject or scientific integrity of the study;
- (6) Other contributing factors to cognitive impairment such as uncontrolled hypothyroidism (TSH >10 mU/l) or untreated low vitamin B12 (<250 ng/mL);
- (7) Uncontrolled congestive heart failure reflected by poor exercise tolerance and shortness of breath at rest or with some exertion;
- (8) Actively undergoing chemotherapy or radiation therapy for cancer treatment;
- (9) History of stroke in the past 3 years;

- (10) Severely impaired cognition (MoCA ≤10, FAST >5 or CDR >2);
- (11) Inability to have MRI and LP e.g. for MRI, metal implants or cardiac pacemaker or for LP, bleeding diathesis from disease states or from use of anticoagulants such as warfarin, heparin and related products, Rivaroxaban or Xarelto, Apixaban or Eliquis, Edoxaban or Savaysa, Dabigatran or Pradaxa. Subjects who can have either one LP or MRI will be enrolled;
- (12) Inability to have cognitive assessment due to hearing, vision, or language issues or due to severe impairment;
- (13) History of increased intracranial pressure (ICP);
- (14) In those who are unable to demonstrate that they understood the details of the study using the UBACC modified for EMERALD (i.e. lack of decisional-capacity to consent), a study partner/surrogate who can sign on their behalf will be required; otherwise, they will be excluded;
- (15) Use of phenobarbital or rifampin due to drug interaction.

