6.8. BLOOD CHEMISTRIES AND BLOOD COUNT

Blood will be drawn at various visits. Please refer to **Table 1** for specific tests done at each visit.

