9.3. DATA ANALYSIS

Table 2 provides a list of main outcomes.

Table 2. Independent, main outcome and other variables to be used in the analyses	
Independent:	Group (Montelukast vs placebo)
Safety outcome:	GI symptoms (diarrhea, nausea, vomiting), anaphylaxis, elevated liver enzymes, PT/INR, behavioral changes, seizures, number of discontinuations from Montelukast, treatment-emergent AE/SAE, deaths
CSF outcomes:	CSF amyloid and tau, inflammatory proteins
Vascular outcomes:	PWV/PWA
Imaging outcomes:	Perfusion, hippocampal volume
Cognitive outcomes:	CDR, NIH Toolbox Cognition battery (NIHTB-CB)

Baseline characteristics including demographic, social and cognitive measures will be compared between the 2 groups to assess randomization fidelity. The list of the main variables is shown in Table 2. We will compare the change in our outcomes over the study period between the treatment and placebo arms using Mixed Models. For the dose response analysis, the dose vs cysLT-1 receptor activity will be plotted to explore the degree of cysteinyl leukotriene modulation at the various doses.

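### PT/INR is a listed safety outcome, but no follow-up visit measures it in everyone, and the one conditional month-12 check depends on an undefined baseline

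*Combined protocol and SAP*

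**What the plan says.** Section 9.3 introduces Table 2 as the list of main outcomes. Its safety row includes "anaphylaxis, elevated liver enzymes, PT/INR, behavioral changes, seizures". The analysis text below it reads: "We will compare the change in our outcomes over the study period between the treatment and placebo arms using Mixed Models".

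The measurement schedule is in Table 1 and its footnotes, and section 6.8 refers the reader to that table "for specific tests done at each visit".

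- **Screening:** "Screening labs include: CBC, CMP (BUN, Cr, electrolytes, liver function test (LFT)), B12, TSH and PT/INR".
- **Follow-up:** "Safety labs at 6 weeks, 3, 6 and 12 months include CBC, CMP (BUN, CR, electrolytes, liver function test". PT/INR is not named.
- **Month 12, conditional:** the footnote attached to the month-12 CSF entry applies to a participant who "did not have PT/INR done at baseline or started taking any blood thinners during the study, PT/INR will be done before LP".

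Section 4.2 bears on this in two places. Item 4 excludes an INR above 1.9, so a value is needed before enrolment. Item 11 gives "bleeding diathesis from disease states or from use of anticoagulants such as warfarin, heparin and related products" as examples of why an LP may not be possible, and it admits participants who can have only one of LP and MRI.

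**The concern.** A comparison of change needs a pre-treatment value and a follow-up value in both randomised arms. The schedule supplies the first for everyone and the second only under a condition. That condition was written as a check before a procedure, not as a way of measuring an outcome. Which participants it catches depends on a word that the footnote does not define.

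Safety is part of the primary objective, and section 7.1 names a raised bleeding tendency among the rare potential complications of the drug. If the schedule is followed exactly, a named safety outcome is left largely or partly unmeasured.

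**Working it through.** The plan states no figure for this outcome, so there is none to reproduce. The check sets the schedule against the outcome list and then sizes the result.

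**Step 1. Count the scheduled tests.** Follow-up visits are at 6 weeks and 3, 6 and 12 months. Unconditional PT/INR tests after randomisation: 0 of 4.

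**Step 2. Read the month-12 footnote both ways.**

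*Reading A: baseline means any pre-treatment value.* Because of the INR exclusion, nearly every participant should have a screening value, so the first trigger is almost empty. Anyone it does catch has a month-12 value only and no change score. Pairs then come only from participants who start a blood thinner. Some of them may be unable to have the LP, and then they have no test either.

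*Reading B: baseline means the month-0 visit.* Table 1 places no PT/INR there, so nearly everyone meets the first trigger and the blood-thinner trigger adds nothing. Everyone who has the month-12 LP is tested; those without an LP are missed.

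**Step 3. Weigh the readings.** The FAQ footnote treats baseline and screening as separate visits ("FAQ will be skipped at baseline if already done at screening visit"), which supports B. Against that, section 5.1 judges the 6-week liver enzymes against baseline levels, although Table 1 schedules pre-treatment liver tests only at screening; this supports A. B also makes the footnote's condition true for almost everyone, so there would be little reason to write a condition. A is the more plausible, but each reading leaves one trigger nearly idle and the text does not settle it.

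**Step 4. Size of the loss.** Section 3 gives 30 completers, 15 per arm. The documents give no rate of starting blood thinners and no rate of missing the month-12 LP, so both are assumed over a range.

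Reading A, with start rate *p*:

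- Expected pairs, at most 30 × *p*.
- Chance that at least one arm of 15 has fewer than two pairs = 1 − [1 − F(1; 15, *p*)]², where F is the binomial distribution function.

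| Assumed *p* | Pairs of 30, at most | Chance at least one arm has fewer than 2 |
|---|---|---|
| 5% | 1.5 | 97% |
| 10% | 3 | 80% |
| 20% | 6 | 31% |

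Reading B, with an assumed 10%, 20% or 40% having no month-12 LP: 30 × 0.90 = 27, 30 × 0.80 = 24, or 30 × 0.60 = 18 pairs.

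95% confidence interval half-width for the difference in mean change, in SD of change = t(0.975; 2n − 2) × √(2/n), with n per arm:

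| n per arm | Situation | Calculation | Half-width (SD) |
|---|---|---|---|
| 15 | all completers tested | 2.048 × 0.365 | 0.75 |
| 12 | B, 20% without LP | 2.074 × 0.408 | 0.85 |
| 9 | B, 40% without LP | 2.120 × 0.471 | 1.00 |
| 3 | A, 20% start, split evenly | 2.776 × 0.816 | 2.27 |

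The last row is the favourable case under A. Even there, the pairs are a subgroup formed after randomisation whose PT/INR may be altered by the newly started drug. A mixed model does not help, because follow-up values exist by design only in that subgroup.

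**The case against.** - **Table 1 does have a column headed baseline at month 0**, and neighbouring footnotes use the word for that visit. Literal consistency therefore favours Reading B, under which most participants are tested. This stands as a reason not to treat Reading A as settled. It does not remove the defect: B still misses participants without an LP and makes half of the footnote redundant.
- **Most entries in the Table 2 safety row are events or counts**, so PT/INR may be meant as an abnormal-result event and not as a mean change. That is fair, and the half-widths apply only if change is what is analysed. An abnormal result still has to be measured, however, so the gap in the schedule is the same.
- **The follow-up footnote says the labs include CBC and CMP, which might be open-ended.** The screening footnote uses the same verb and names PT/INR. If PT/INR were routine at month 12, the conditional footnote would serve no purpose.
- **Bleeding would be caught in other ways:** adverse-event recording, CBC at every follow-up visit, and repeat blood tests at the physician's discretion under section 7.4. These limit the consequence, but none supplies PT/INR systematically in both arms.
- **Even full testing gives a half-width of 0.75 SD**, so little could be concluded about a rare effect. True, but that would be an imprecise randomised comparison, whereas Reading A gives none.

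**Conclusion.** The concern holds. PT/INR is named as a safety outcome, yet the plan requires no follow-up measurement in all participants. On the more plausible reading there is no usable between-arm comparison of change. On the other, the comparison is limited to participants who have the month-12 LP: 18 to 27 of 30 if 40% to 10% have none.

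The conclusion rests on the schedule alone; the assumed rates only illustrate its size. Confidence is medium because the meaning of baseline in the footnote is open. PT/INR is one of many safety items and liver tests are scheduled at every follow-up visit, so this should be corrected but does not undermine the safety assessment as a whole.

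**What to change.** State in the month-12 footnote whether baseline means the screening value or the month-0 visit, and reconcile that footnote, the safety-lab footnote and Table 2. Then choose one of two options.

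- **Keep PT/INR as an outcome.** Add it to the month-12 blood draw for all participants, including those without an LP. Name the screening value as the baseline, analyse as randomised, and add a sensitivity analysis for participants who started a blood thinner. The cost is one more test on blood already scheduled to be drawn. A month-12 visit held remotely under section 6.10.2 may still leave a value missing.
- **Remove PT/INR from the Table 2 safety outcomes** and leave bleeding to adverse-event recording. This adds no test, but no coagulation test then remains among the safety outcomes.

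Either option needs one sentence defining baseline and, under section 11.1, IRB review of the modification. The check before the LP is a separate clinical matter, and no change to it is proposed.

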1. STUDY OBJECTIVES

Our primary objective is to determine the safety and dose-response for and target engagement of the treatment with escalating doses of Montelukast in those with mild cognitive impairment (MCI) or early Alzheimer's disease (AD) dementia based on cognitive and functional evaluation.

Our secondary objectives are to assess the efficacy and estimate the effect size of up to 1-year treatment of Montelukast on biomarkers of neurodegeneration and neuro-inflammation, and vascular function; and to estimate the effect of Montelukast on cognitive function, functional measures, and vascular inflammatory and endothelial markers in MCI/early AD dementia.

[figure not shown]
2. BACKGROUND AND RATIONALE

Therapeutic options for AD remain limited, especially treatments linking neurovascular and neuro-inflammatory changes with clinical manifestations of disease.¹ Prior research studies have documented a positive effect of cysteinyl leukotriene type 1 (cysLT-1) receptor antagonist, particularly Montelukast, on neuro-inflammatory processes and neuronal injury, blood brain barrier (BBB) integrity, and amyloid- β 42 (A β) accumulation. Although Montelukast is currently in use for the treatment of inflammatory diseases e.g. bronchial asthma and exercise-induced bronchospasm, its effect on cognitive function and AD biomarkers however, is yet to be fully understood.

endothelium following brain injury in rats and humans.^{16,17} In adult rat neural progenitor cells, blockade of cysLT-1 and GPR17 receptors was found to increase neural stem and progenitor cell proliferation, suggesting a potential for neurogenesis and restoration of BBB integrity.¹⁸ Previous work suggests that CysLT-1R antagonists attenuate cerebral ischemia, reduce astrocytic proliferation and glial scar formation, and restore microvascular endothelial function.^{19,20} In MCI and AD, inhibition of cysLT-1R signaling may translate into improved cognition. This multi-target characteristic of CysLT-1R antagonists increases the likelihood of producing a disease-modifying effect for prodromal and early Alzheimer's disease.

2.2. SAFETY OF RECEPTOR-SPECIFIC LTRA IN MCI AND EARLY AD

Multiple research studies have shown that Montelukast has a good safety profile with respect to adverse events.²¹ In placebo-controlled dose-ranging studies conducted by the Montelukast Asthma Study Group, adult participants were randomly assigned a placebo or Montelukast at daily doses ranging between 2 mg and 200 mg for the treatment of chronic asthma. Authors found that adverse events were not dose-related, and were similar between placebo and Montelukast treatment groups.^{22,23} Furthermore, in a pediatric study, doses of Montelukast up to 536 mg were found to not yield any serious side effects and could be administered from home.²⁴ Although the US Food and Drug Administration (FDA) has issued warnings linking Montelukast and suicidality, extensive systemic reviews of Montelukast and suicidality have yielded inconclusive findings. In a post-marketing review of adverse events (AE) conducted for the FDA by Merck (116 clinical trials, n=20,131), no completed suicides were reported. In addition, suicide risk was rare and did not differ between the Montelukast and placebo groups.^{25,26}

Prior animal studies in young and older rats showed improved task learning skills among older rats with learning and memory deficits and taking oral Montelukast (10mg/kg body weight).²⁷ A case series report of 17 study subjects with cognitive impairment who were taking 80 mg total oral daily dose of Montelukast suggested subjective memory improvement. More importantly, subjects did not report any side effects or adverse reactions for the administered Montelukast dose.²⁸

2.3. STUDY RATIONALE

In the brain, cysteinyl leukotrienes bind cysLT-1R and cysLT-2R. CysLT-1 receptor inhibition decreases oxidative stress,²⁹ improves endothelial function and cerebral perfusion, and decreases cholinergic depletion, neuro-degeneration, and memory loss.^{28,30-33} CysLT-1R antagonists affect multiple systems involved in AD including vascular and neural progenitor cell function, A β -triggered neurotoxicity and tau hyperphosphorylation.^{18,34} CysLT-1R blockade using Montelukast, influences crucial steps in A β -induced cognitive decline, restoration of BBB integrity, neuronal injury and neurogenesis by inhibiting neuro-inflammation and apoptosis.^{20,27} Use of Montelukast in this human trial will address knowledge gaps in long-term administration of the drug, and in its future clinical translation for AD treatment.

3. STUDY DESIGN

This is a **PHASE II**, 1-year double-blind placebo-controlled randomized clinical trial where participants will be treated with Montelukast (escalating doses: 10, 20 to 40 mg) or matched placebo. The study will enroll 36 participants to account for an expected 20% drop-out rate in order to achieve a sample size of 30 with 15 participants in each group.

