5. STUDY INTERVENTIONS

5.1. INTERVENTIONS, ADMINISTRATION, AND DURATION

Participants will be randomized to either Montelukast or placebo in a 1:1 fashion. All participants will be initiated on 10 mg. The dose will be increased in 2-week increments to 20 mg and 40 mg as long as participants report no intolerable symptoms or adverse events (e.g. jaundice, headache, GI symptoms, and neuropsychiatric changes), and liver enzymes checked at 6 weeks do not exceed 3X baseline levels. If participant had positive LFT change (3x increase), dose will be decreased to the prior level (20 mg or matched placebo) and LFT rechecked 2 weeks later. If LFT increases further, then dose will be decreased to 10 mg or matched placebo. If LFT are still increased 2 weeks after 10 mg or matched placebo, study medication will be discontinued. Treatment will be provided in similar capsules format to be taken orally 1-2 times a day. Investigators, study personnel and participants will be blinded for drug assignment. Participants will be treated for 1 year.

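### Section 3: enrolling 36 with 20% drop-out leaves about 29 participants, not the stated 30 (15 per group)

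*Combined protocol and SAP*

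**What the plan says.** The sample size is given in two places.

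- **Section 3 (Study Design)** gives enrolment, drop-out and target in one sentence: "The study will enroll 36 participants to account for an expected 20% drop-out rate in order to achieve a sample size of 30", which it splits as 15 per group.
- **The précis, under Sample Size and Population,** says only: "Our sample size is 30 for this trial". It does not say whether 30 means enrolled or completing.

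Section 5.1 sets the allocation: "Participants will be randomized to either Montelukast or placebo in a 1:1 fashion". Section 9.3 gives the analysis: "We will compare the change in our outcomes over the study period between the treatment and placebo arms using Mixed Models". The document gives no inflation formula, no definition of drop-out, no rule for replacing participants who leave, and no power or precision calculation.

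**The concern.** A reader who takes 20% off 36 does not get 30. The sentence in section 3 is the only account of how the sample size was reached, and its figures do not lead to the number it states.

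The retained number matters more for some outcomes than for others. Under Table 1, the cognitive battery and LTE₄ are measured at baseline, 6 and 12 months, so a participant who leaves after month 6 still adds follow-up data to a mixed model. CSF, brain MRI and PWV/PWA are scheduled only at baseline and 12 months. For those outcomes, a participant who leaves the study before the final visit has no follow-up value, so the number retained caps the number with a measured change.

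**Working it through.** **Inputs**

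- Planned enrolment: 36 (section 3).
- Expected drop-out: 20% (section 3).
- Target after drop-out: 30, as 15 per group (section 3); 30 in the précis.
- Allocation: 1:1 (section 5.1), so 18 per arm.

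**Step 1. Reproduce the plan's figure.** Adding 20% to the target gives 30 × 1.20 = 36, an exact match. This applies the drop-out rate to the target, whereas drop-out happens among those enrolled.

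**Step 2. Apply 20% to those enrolled.** Retained = enrolled × (1 − d).

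- Total: 36 × 0.80 = 28.8.
- Per arm: 18 × 0.80 = 14.4.

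**Step 3. Solve for each figure, holding the other two.**

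| Hold fixed | Solve for | Result |
|---|---|---|
| 36 enrolled, 20% drop-out | retained | 36 × 0.80 = 28.8 (14.4 per arm) |
| 36 enrolled, 30 retained | drop-out | 1 − 30/36 = 16.7% |
| 30 retained, 20% drop-out | enrolled | 30/0.80 = 37.5, so 38 (19 per arm) |

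**Step 4. Size of the gap.**

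- Shortfall: 30 − 28.8 = 1.2 participants; 1.2/30 = 4%.
- Confidence interval width, same SD: √(30/28.8) = 1.021, about 2% wider.

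**Step 5. Chance of keeping at least 30 (illustration).** This assumes that participants drop out independently. Of the rates below, only 20% comes from the plan.

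| Enrolled | Drop-out | P(at least 30 retained) |
|---|---|---|
| 36 | 15% | 71% |
| 36 | 16.7% | 61% |
| 36 | 20% | 40% |
| 36 | 25% | 17% |
| 38 | 20% | 66% |

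At the plan's own rate, 30 is more likely to be missed than reached.

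**The case against.** Several points can be made for leaving the text alone.

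- **The rate is an expectation and 30 is an aim.** Thirty could still be reached, with a chance of about 40% under the illustration above. That is true. But a sample size adjusted for an expected rate should give the target when that rate occurs, and this one does not.
- **36 may have been meant as a 20% margin on the target.** That explains the figure but does not justify it, because the text calls the 20% a drop-out rate.
- **Drop-out is undefined, and stopping the drug is not leaving the study.** Section 5.3.1 keeps participants who start a leukotriene antagonist clinically in follow-up. Section 7.4 follows those who stop treatment after an adverse event, and invites them to the full final visit if they have been in the study for more than 5 months. So the loss of 12-month CSF, MRI and PWV/PWA values applies to withdrawal from the study. That limits the consequence and leaves the arithmetic as it is.
- **The retained count is not the analysed count.** Section 9.1 plans intention-to-treat as well as per-protocol analyses. Exclusion criterion 11 (section 4.2) also admits people who can have only one of LP and MRI, so CSF and MRI numbers may fall below 30 whatever the drop-out. Both points stand. They are reasons to state the retained number carefully.
- **The discrepancy is small.** This is correct, and it is why the remedy is limited to wording.

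**Conclusion.** The concern holds. The plan's own enrolment and drop-out figures give 28.8 expected participants (14.4 per arm), not 30 (15 per arm). Rounding does not explain it: 28.8 rounds to 29.

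The result rests only on reading the drop-out rate as a share of those enrolled, which is its ordinary meaning, and on nobody being replaced, since the document has no replacement rule. Only the probabilities of retaining 30 need independent drop-out.

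The effect is about one participant. The effect on power cannot be derived from the plan, which gives no alpha, effect size or SD, and no stated target is breached. This is a figure that should be corrected, not a threat to the trial.

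**What to change.** Keep enrolment at 36 and restate section 3 in one of two ways:

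- *36 enrolled; about 29 expected after 20% drop-out (14 to 15 per arm)*; or
- *36 enrolled, which retains 30 (15 per arm) if overall drop-out is at most 16.7% and losses are equal between arms*.

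Then align the précis. If section 3 keeps the 20% rate, the précis figure of 30 becomes 36 enrolled with about 29 expected to complete. If section 3 states the 16.7% limit, 30 can stay if it is labelled as the number retained.

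The cost is a wording change in section 3 and the précis. Either the stated retained number falls by about one, or the drop-out allowance becomes 16.7%. Keeping both 30 and 20% would mean enrolling 38, but with no power or precision target resting on 30, the correction does not require it. Procedures, randomisation and analysis do not change.
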